4.1. General Considerations

Data will be analyzed using SAS 9.4 or R. In the ITT/Safety population, ACP (ARC1905 2mg), Sham will be used as treatment groups. Subjects who were discontinued from the study in Year 1 will be included. In the Re-randomized population, ARC1905 2mg EM, ARC1905 2mg EOM, and Sham will be used as treatment groups.

Descriptive statistics will be tabulated as follows:

Categorical data will be summarized in contingency tables presenting frequencies and percentages.

Continuous data will be summarized using number of non-missing values (n), mean, standard deviation, median, minimum, 1st quartile (Q1), 3rd quartile (Q3), and maximum values.

Graphic display and visualization will be utilized to summarize descriptive statistics.

4.1.1. Visit Windows

The scheduled visits will be used in the analyses over time.

Missing scheduled follow-up visit will be substituted by an unscheduled or early withdrawal visit occurring within each follow-up visit window if there is only one unscheduled or early withdrawal visit occurring within the window. If there are multiple unscheduled or early withdrawal visits occurring within the window, the closest one within the visit window will be used. If no unscheduled or early withdrawal visit occurred within the window, the visit will be considered as missing. The details are tabulated in the Supporting Document section.

4.1.2. Handling Missing Data in Efficacy Analyses

Methods that take into account the presence of missing data and that yield valid estimates under the assumption of data missing at random (MAR) will be used. The Mixed Model on Repeated Measures fitted by Restricted Maximum Likelihood method will be used in the mean growth GA analysis, where the observed data will be used with no imputation. Several imputation methods will be used in sensitivity analyses, whenever necessary, to impute the missing data, as described in Section 4.2.4 sensitivity analyses.

4.1.3. Handling Missing Data in Descriptive Analyses

When summarizing categorical variables, subjects with missing data are generally not included unless otherwise specified. When needed, the category of “Missing” is created and the number of subjects with missing data is presented.

When summarizing continuous variables, subjects with missing data are not included in calculations. No imputations are made.

4.1.4. Handling Missing or Partially Missing Dates

Missing or partially missing dates will not be imputed at data level. However, assumptions for missing or partially missing dates for important variables will be made to allow inclusion of appropriate data records in the analyses. In general, the assumptions about the missing or partially missing dates, when needed, are made conservative to avoid overestimation of treatment effect and underestimation of adverse effects.

If a medication date or time is missing or partially missing, so it cannot be determined whether it was taken prior or concomitantly, it will be considered both as a prior and a concomitant medication.

If the partial AE onset date information does not indicate whether the AE started prior to treatment or after treatment, the AE will be classified as after the start of treatment.

CCI [REDACTED]

[REDACTED]

[REDACTED]

- [REDACTED]
- [REDACTED]

[REDACTED]

[REDACTED]

- [REDACTED]

[REDACTED]

4.1.6. Disposition of Subjects

The number of subjects randomized and treated, by treatment arm will be presented. The reason for exclusion from one or more analysis sets will be summarized.

The number of subjects re-randomized and treated post-randomization, by treatment arm will also be presented.

The frequency of premature discontinuations from the study treatment prior to study completion (Month 24) will be given by treatment arm and overall. The details of the ‘Adverse Event’,

'Protocol violation', 'Investigator decision', 'Sponsor Decision', 'Subject request', 'Lost to Follow-Up', 'Subject Non-Compliance', or 'Other' will be included in a listing.

The frequency of premature discontinuations from the study prior to Month 24 will be given for the ITT population and re-randomized population, by treatment arm and overall. The primary reason for non-completion of the study will be summarized.

4.1.7. Treatment Misallocation

For subjects with errors in treatment allocation, the following is described under which treatment groups they will be reported for efficacy and safety analyses:

For example, if subjects were:

- Randomized (regardless of error) but not treated, then they will be excluded for all efficacy and safety analyses. These subjects will be included in the summary of subject dispositions.
- Treated but not randomized, then by definition they will be excluded from the efficacy analyses since randomization is missing but will be reported under the treatment they actually received for all safety analyses.
- Randomized but were administered the incorrect treatment at any time during the study, then they will be reported under their randomized treatment group for efficacy analyses on ITT population but will be reported under the treatment they actually received for all safety analyses on SAFETY population (see Section 3.2.3); specifically, this implies that for safety analyses, a patient who ever received ACP will be included in the ACP group based on actual injections received.
- Re-randomized population will be used for both efficacy and safety analysis in Year 2 with the treatment as re-randomized.

4.1.8. Protocol Deviations

All protocol deviations will be assessed and identified prior to database lock in a masked fashion to determine whether they are major by the sponsor. The final list of major protocol deviations will be provided prior to the database lock.

The major protocol deviations will be summarized for the ITT population and re-randomized population. The details will be listed by subject and by treatment arm.

4.1.9. Demographic and Baseline Characteristics

Descriptive statistics will be provided on Baseline information including demographics and disease characteristics. No tests of significance will be conducted.

Descriptive statistics with respect to subject characteristics at Baseline will be displayed for the ITT population and re-randomized population. When several measurements are available before the first administration of study drug, the Baseline value is the last available value prior to first

dose, except for the Baseline visual acuity score which is the mean of the Screening and Day 1(D0) values if both are available.

The variables to be summarized are:

- Gender, ethnicity, race, iris color, age, current smoking status.
- Prior ocular history, both eyes (by MedDRA preferred term, including number and percentage of all subjects with at least one prior ocular history)
- Medical history (excluding ocular history) (by body system and preferred term, with number and percentage for both; including number and percentage of all subjects with at least one prior medical history)
- Prior surgeries/procedures (by body system and preferred term, with number and percentage for both; including number and percentage of all subjects with at least one prior surgery/procedure)
- Vital signs (height, weight, pulse, blood pressure)
- ECOG performance status
- Pregnancy test
- Visual acuity (ETDRS), study eye
- Tonometry, study eye
- ECG
- Ophthalmic exam, both eyes (motility, lids/lacrimal/lashes, conjunctiva/sclera, cornea, anterior chamber activity: cells, iris, pupils, lens status, vitreous haze, vitreous hemorrhage, posterior vitreous detachment, optic nerve, macula, retinal vessels, peripheral retina)
- Fundus autofluorescence (FAF) imaging assessments, study eye
- Fluorescein angiography (FA) imaging assessment

4.1.10. Prior and Concomitant Medications

All prior and concomitant medications will be summarized separately by WHO Drug code (WHO Drug Dictionary, released on 1 September 2020) on the ITT population and re-randomized population. Medication usage will be summarized according to the 2nd level (main therapeutic level) and the 4th level (preferred term level) Anatomic Therapeutic Chemical (ATC) classification. Subjects will only be included once in the summaries within each ATC 2nd level or ATC 4th level category. The summaries will include the number and percentage of all Subjects with at least one prior or concomitant medication, respectively.

4.2. Efficacy Analysis

4.2.1. Mean GA growth (slope): EM, EOM vs. Sham

4.2.1.1. Definition of Estimand

The objective is to demonstrate efficacy of ACP EM or EOM versus Sham in mean GA growth rate (slope) after re-randomization regardless of any non-adherence to or interruption of study treatment, and regardless of initiation of alternative treatment.

The following 5 attributes define the Estimand for the objective evaluation:

A. Population: re-randomized population

B. Interventions:

ACP EM or EOM versus Sham.

C. Endpoint:

GA area over 24 months from Baseline, Month 6, Month 12, Month 18, and Month 24.

D. Intercurrent events (ICE's) and strategies:

1. Treatment changes (i.e., interruptions, non-adherence, dose changes, discontinuation): “treatment policy” – i.e., treatment changes will be ignored, and all data collected will contribute to the analysis regardless of whether these follow such ICE's.
2. COVID-19: “treatment policy” – i.e., impact of COVID-19 pandemic will be ignored, and all data collected will contribute to the analysis regardless of whether these follow such ICE's.

E. Population-level summary:

Difference between groups (EM vs. Sham, EOM vs. Sham) in mean growth rate (slope) of the GA area over 24 months.

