A brief SAP addendum (version 1.0) for cumulative Year 2 data of ISEE2008 study was approved on 3 August 2022 before the unmasking of Year 1 data for primary analysis. The addendum prespecified mainly sequential statistical testing procedure on Year 2 (Supporting Document).

The purpose of this SAP (Year 2) is to expand the addendum to provide technical details for the Year 2 and the final analysis of the study.

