1.1. Objectives and Endpoints

Efficacy objectives and corresponding Endpoints are tabulated below

Efficacy objectives	Endpoints

 • Demonstrate ACP 2mg in EM or EOM intravitreal injection after re-randomization reduces GA growth (slope) compared to Sham in patients with geographic atrophy secondary to age-related macular degeneration (AMD) up to Year 2. • Demonstrate ACP 2mg intravitreal injection reduces rate of persistent vision loss (BCVA) compared to Sham up to Month 24 	
 • GA area measured by FAF in 5 time points: Baseline, Month 6, Month 12, Month 18, and Month 24. • Time to vision loss (defined as BCVA loss \geq 15 letters from baseline at two or more consecutive visits up to Month 24).

 • [REDACTED] CCI [REDACTED] 	
 • [REDACTED] • [REDACTED] • [REDACTED]

Safety
	

 • Safety of ACP 2mg in EM or EOM intravitreal injection compared to Sham in patients with geographic atrophy secondary to age-related macular degeneration (AMD) up to Year 2. • Safety of ACP 2mg intravitreal injection compared to Sham in patients with geographic atrophy secondary to age-related macular degeneration (AMD) up to Year 2. 	
 • Adverse events (AEs) • Serious adverse events (SAEs) • Vital signs (pulse, systolic and diastolic blood pressure) • Ophthalmic variables (ophthalmic examination, best corrected visual acuity (BCVA), low luminance BCVA (LLBCVA), intraocular pressure (IOP)) • Electrocardiography (ECG) • Laboratory variables (blood: hematology, renal function, hepatic function, and electrolytes; urinalysis)

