1.3. Study Period and Visit Window Definition

Study assessments in Year 2 are summarized below.

Year 2

2. Statistical Hypotheses

The following hypothesis testing will be conducted sequentially.

1. Hypothesis testing in EM vs. Sham for mean GA growth rate are:

$$H_0: \Delta = 0$$

$$\text{versus } H_1: \Delta \neq 0,$$

where $\Delta = \mu_1 - \mu_2$, μ_i is the mean growth rate (slope) of GA over 24 months for treatment EM, or Sham, respectively.

2. Hypothesis testing in ACP 2mg vs Sham for time to vision loss will be conducted using Kaplan-Meier method with a log-rank test
3. Hypothesis testing in EOM vs. Sham for mean GA growth: similarly, as in (1)
4. Hypothesis testing in ACP 2mg vs Sham for mean change in best corrected visual acuity (BCVA in ETDRS letters) from Baseline to Month 24
5. Hypothesis testing in ACP 2mg vs Sham for mean change in low luminance best corrected visual acuity (LL BCVA in ETDRS letters) from Baseline to Month 24

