4.2.1.2. Statistical Method

With a re-randomization at the end of Year 1, the initial stratification factors from the randomization are no longer applicable in the analysis of Year 2. Therefore, the stratifications factors will be removed from the MMRM model as in the primary analysis.

The revised model is described below.

A mixed model for repeated measures (MMRM) will be applied to all available data, using response variable of the GA growth area over time up to Month 24 in 5 time points: Baseline, Month 6, Month 12, Month 18, and Month 24. The MMRM will be used to assess the difference between the treatment groups in terms of the rate of growth (slope) of the GA over time of 24 months. Time is defined as a continuous variable in number of study days since the baseline assessment. Treatment groups include ACP EM, ACP EOM, and Sham. A model will be fitted

by using restricted maximum likelihood (REML) and include time, treatment, and treatment by time interaction as fixed effects, subject as random effect.

Notice that in the primary analysis at Year 1 (Month 12), the square root transformation of GA growth area was used. However, the mean GA growth (slope) has shown similar results with or without square root transformation. In addition, it is difficult to interpret the transformed data in context. Therefore, in the Year 2 analysis, the untransformed GA growth using observed GA area of measurement will be used as the primary endpoint.

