4.5. Changes to Protocol-planned Analyses

The following changes are made from protocol planned analyses:

- Time to vision loss analysis based on BCVA was added after primary analysis on Year 1
- GA growth rate without square root transformation
- Piece-wise analysis by every 6-month interval on GA growth rate

5. Supporting Documentation

5.1. [Redacted] *CCI* [Redacted]

[Redacted]

[Redacted]	[Redacted]	[Redacted]
[Redacted]	[Redacted]	[Redacted]
[Redacted]	[Redacted]	[Redacted]
[Redacted]	[Redacted]	[Redacted]
[Redacted]	[Redacted]	[Redacted]
[Redacted]	[Redacted]	[Redacted]
[Redacted]	[Redacted]	[Redacted]
[Redacted]	[Redacted]	[Redacted]
[Redacted]	[Redacted]	[Redacted]
[Redacted]	[Redacted]	[Redacted]
[Redacted]	[Redacted]	[Redacted]
[Redacted]	[Redacted]	[Redacted]
[Redacted]	[Redacted]	[Redacted]
[Redacted]	[Redacted]	[Redacted]
[Redacted]	[Redacted]	[Redacted]

CCI

[REDACTED]	[REDACTED]	[REDACTED]
[REDACTED]	[REDACTED]	[REDACTED]
[REDACTED]	[REDACTED]	[REDACTED]
[REDACTED]	[REDACTED]	[REDACTED]
[REDACTED]	[REDACTED]	[REDACTED]
[REDACTED]	[REDACTED]	[REDACTED]
[REDACTED]	[REDACTED]	[REDACTED]
[REDACTED]	[REDACTED]	[REDACTED]
[REDACTED]	[REDACTED]	[REDACTED]
[REDACTED]	[REDACTED]	[REDACTED]

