5.2. Statistical Analysis Plan Addendum for Cumulative Year 2 Data

Cumulative ISEE2008 year 2 data will be analyzed in a similar way as year 1 data with the following changes.

[figure not shown]

The data will be summarized in 4 groups: Sham, ACP every month (EM), ACP every other month (EOM), ACP overall. ACP overall group will include patients who discontinued from the study in year 1.

If the primary analysis testing GA growth rate (ACP vs Sham) based on year 1 data is statistically significant, the following ranked hypotheses tests will be performed in a sequential way to control familywise type I error rate with 2-sided significance level of 0.05 using similar MMRM specified in year 1 SAP without the stratifications factors. A test will be performed only if all the preceding tests are statistically significant.

1. Mean GA growth rate of ACP EM is lower than Sham based on GA area measured by FAF in 5 time points: baseline, month 6, month 12, month 18 and month 24.
2. Mean GA growth rate of ACP EOM is lower than Sham based on GA area measured by FAF in 5 time points: baseline, month 6, month 12, month 18 and month 24.
3. Mean change in best corrected visual acuity (BCVA in ETDRS letters) from Baseline to Month 24 in ACP is different from Sham based on monthly data from month 1 to month 24.
4. Mean change in low luminance best corrected visual acuity (LL BCVA in ETDRS letters) from Baseline to Month 24 in ACP is different from Sham based on change from baseline data from the following 4 time points: month 6, month 12, month 18 and month 24.

5. [REDACTED] *CCI* [REDACTED]

6. References

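### The Year 2 SAP words the EM/EOM objective as GA slope after re-randomization but tests a Baseline-to-Month-24 slope, so the EOM test alone does not show efficacy after Month 12

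*SAP*

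**What the plan says.** All references are to the Year 2 SAP unless stated.

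- **Objective.** Section 4.2.1.1: "The objective is to demonstrate efficacy of ACP EM or EOM versus Sham in mean GA growth rate (slope) after re-randomization". Section 1.1 has similar wording, "Demonstrate ACP 2mg in EM or EOM intravitreal injection after re-randomization reduces GA growth (slope) compared to Sham", and closes by extending the period up to Year 2.
- **Summary measure.** Section 4.2.1.1: "Difference between groups (EM vs. Sham, EOM vs. Sham) in mean growth rate (slope) of the GA area over 24 months". The endpoint is GA area at Baseline and Months 6, 12, 18 and 24.
- **Hypotheses.** Section 2 defines the EM test on the mean slope over 24 months. The EOM test is third: "Hypothesis testing in EOM vs. Sham for mean GA growth: similarly, as in (1").
- **Model.** Section 4.2.1.2 fits time, treatment and their interaction, with subject as a random effect. "Time is defined as a continuous variable in number of study days since the baseline assessment". There is no change of slope at Month 12.
- **Addendum.** Section 5.2: "Mean GA growth rate of ACP EOM is lower than Sham based on GA area measured by FAF in 5 time points". The Introduction says that the addendum "was approved on 3 August 2022 before the unmasking of Year 1 data for primary analysis".
- **Regimen.** Under section 6 of the protocol, patients assigned to active drug are dosed monthly until Month 12 and only then re-randomized to EM or EOM. Sham patients stay on Sham.
- **Supportive fits.** Section 4.2.1.3.3 (visit as a category) and section 4.2.1.3.4 (6-month pieces) are listed as sensitivity or supportive analyses.
- **Analysis set.** Section 3 defines the re-randomized set as the ITT patients re-randomized at Month 12. It then lists Sham among that set's treatment groups and excludes those who left the study in Year 1.

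**The concern.** The stated objective and the tested quantity cover different periods. For EM this matters less, because the regimen does not change at Month 12. For EOM, the first 12 of the 24 months were on a different regimen from the one the group is named after.

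EOM versus Sham sits third in a hierarchy tested at two-sided 0.05. If a significant result is read against the objective in section 4.2.1.1, it will look like evidence that every-other-month dosing slows growth after Month 12. The test could succeed largely on the Year 1 monthly effect. What is at stake is the claim that the result can carry, not the validity of the p-value.

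The definition of the re-randomized set has a smaller wording fault. Sham patients are never re-randomized, so read literally the definition leaves out the comparator that section 3 then lists.

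**Working it through.** **1. Reproduce the plan's own figure.** The only power figures are for the Year 1 primary comparison (Year 1 SAP, Study Design and Sample Size; protocol 11.3): 0.11 mm, about 200 per arm, 97% power, and significance at an estimated 0.057 mm. No SD is printed, so it is solved from the threshold:

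- SD = (0.057 / 1.96) / √(2/200) = 0.291
- Power = Φ(0.11 / 0.0291 − 1.96) = 96.6%, against 97% stated
- At two-sided 0.01: 88.6%, against nearly 90% stated

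The figures agree with each other. This checks consistency only, because the SD is derived from one of them.

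**2. Weight of each year in the tested slope.** Take t = 0, 0.5, 1, 1.5, 2 years. The least-squares slope weights are −0.4, −0.2, 0, 0.2, 0.4. Let the EOM–Sham difference grow at d1 per year in Year 1 and d2 per year in Year 2.

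- Year 1 part, min(t,1) = 0, 0.5, 1, 1, 1: −0.1 + 0 + 0.2 + 0.4 = 0.5
- Year 2 part, max(t−1,0) = 0, 0, 0, 0.5, 1: 0.1 + 0.4 = 0.5
- Tested difference = 0.5·d1 + 0.5·d2

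The split stays 0.5/0.5 on complete data under random-intercept, random-intercept-plus-slope and AR(1) covariances. If 10%, 20% or 30% of patients miss Month 24 (assumed), the Year 1 weight under a random-intercept model is 0.51, 0.52 or 0.54.

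**3. No EOM effect after Month 12.** With d2 = 0 and d1 = 0.11 mm/yr (assumed, from the design effect), the expected difference is 0.5 × 0.11 = 0.055 mm/yr.

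**4. Chance that the test, taken alone, is significant.** Assumptions: square-root scale, 100 EOM and 200 Sham at full retention. The SD of a 24-month slope is not given, so a range is used. A three-visit slope (weights −1, 0, 1) carries 2 times the measurement-error variance; a five-visit slope carries 0.4 times. If error makes up a share f of the 12-month slope variance, the 24-month SD is 0.291·√(1 − 0.8f).

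- SE = SD·√(1/n_EOM + 1/n_Sham)
- P = Φ(0.055/SE − 1.96)

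| f (assumed) | 24-month SD | SE, 100% retained | P, 100% | SE, 80% retained | P, 80% |
|---|---|---|---|---|---|
| 0 | 0.291 | 0.0356 | 34% | 0.0398 | 28% |
| 0.25 | 0.260 | 0.0319 | 41% | 0.0356 | 34% |
| 0.50 | 0.225 | 0.0276 | 51% | 0.0308 | 43% |

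**5. Why a Month 12–24 contrast needs both scales.** Sham growth implied by OPH2003 (27.38% in protocol 4.3.4; 0.11 mm in protocol 11.3) is g = 0.11/0.2738 = 0.402 mm/yr. Suppose EOM and Sham have equal square-root growth g in Year 2, and EOM lesions are 0.11 mm smaller at Month 12. The Year 2 gain in area still differs by 2 × 0.402 × 0.11 = 0.088 mm²/yr in favour of EOM, whatever the baseline size.

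**The case against.** The strongest reply is that this is mostly wording. Every operative element (endpoint, summary, hypothesis, model, addendum) specifies the same 24-month slope. In section 1.1 the phrase about re-randomization can be read as naming the groups, since the sentence ends with the period up to Year 2. Every EOM patient had a year of monthly dosing first, so the 24-month sequence is the only EOM regimen the trial studies. The interval and visit-wise fits would also show growth after Month 12.

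Much of this stands. The test is valid for the sequence, and the planned fits contain the needed information. But section 4.2.1.1 ties the phrase to the slope itself. Even on the milder reading the test does not isolate Months 12–24. The supportive fits lie outside the hierarchy, and the visible text names no Month 12–24 EOM-versus-Sham contrast. Some items are redacted, including hypothesis 6, so nothing can be said about those.

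A reader might infer that the type I error is inflated. It is not: the stated null concerns the 24-month slope, and a non-zero Year 1 effect makes that null false.

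A reader might also take 28–51% as the chance of a misleading confirmatory EOM result. It is not that either. Under sections 2 and 5.2, EOM is tested only if the Year 1 primary, EM and time-to-vision-loss tests all succeed.

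**Conclusion.** The point holds as a mismatch between the stated objective and the tested quantity. A significant hypothesis 3 would show that 12 months of monthly dosing followed by every-other-month dosing differs from Sham over 24 months. By itself it would not show EOM efficacy after Month 12.

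The equal weighting of the two years needs complete data but no assumed effect size or SD. The 0.055 mm/yr and the 28–51% are illustrative. They rest on the square-root scale, an assumed Year 1 effect of 0.11 mm/yr, 100 against 200 patients, a 24-month slope SD between 0.225 and 0.291, and 80–100% retention. The Year 2 endpoint is untransformed area, for which the documents give no SD.

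The documents do not support saying that the sponsor will claim EOM efficacy after Month 12; they only leave room for that reading. Severity is minor to moderate. The Year 1 primary analysis is not affected.

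**What to change.** 1. **Reword the objective** in sections 1.1 and 4.2.1.1. Label hypotheses 1 and 3 as 24-month effects, with hypothesis 3 as the effect of monthly dosing for 12 months followed by every-other-month dosing. Keep the addendum's five-time-point test and its place. Cost: wording only.

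2. **Name one supportive Month 12–24 EOM-versus-Sham slope contrast**, from a model with a knot at Month 12 or from the fits in sections 4.2.1.3.3 and 4.2.1.3.4, on both the untransformed and square-root scales. Any statement about effect after re-randomization should rest on it. State two caveats: a persisting Year 1 effect can enter it, and on untransformed area so can Month 12 differences in lesion size (working, step 5). It needs no new visits. Disclose that it was added after Year 1 unmasking, as section 4.5 already does for another analysis: "Time to vision loss analysis based on BCVA was added after primary analysis on Year 1". If its SD is again 0.291, its power at 100%, 90% and 80% retention is about 87%, 83% and 79% for 0.11 mm/yr, and 61%, 57% and 52% for 0.08 mm/yr. A non-significant result should not be read as absence of effect.

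3. **Correct the re-randomized set's definition** in section 3 to say that Sham patients still in the study at Month 12 are included. An EM/EOM analysis on all ITT patients is not a usable addition: active-arm patients who left in Year 1 have no EM or EOM assignment, and section 5.2 places them only in the overall active group. Cost: one sentence.
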